7.6 Description of Subgroups to be Analyzed

The primary endpoint will be summarized using the following subgroups of interest:

- Number of previous lines of therapy (0-2 vs. ≥ 3)
- Response to previous treatment (non-responders vs. relapsed)
- Splenectomized subjects vs. non-splenectomized subjects and
- Subjects with baseline platelet count $< 15,000/\mu\text{L}$ versus subjects with platelet count between $15,000/\mu\text{L}$ to $30,000/\mu\text{L}$.
- Subjects with prior TPO-receptor agonist use versus subjects without prior TPO-receptor agonist use.

7.7 Statistical Analysis Methodology

Statistical analysis will be performed using SAS software Version 9.4 or later. The results for each efficacy endpoint will be summarized by visit and treatment for all subjects within the ITT analysis set using descriptive statistical methods. Continuous variables (quantitative endpoints) will be summarized using the mean, the standard deviation (SD), median, range (minimum value and maximum value), and interquartile. Categorical variables (qualitative endpoints) will be summarized using frequency counts (number) and percentages. Data will be listed in data listings.

Details of the statistical analyses, methods, and data conventions will be described in the statistical analysis plan.

All statistical tests will be 2-sided using a 5% significance levels, leading to 95% (2-sided) confidence intervals (CIs). This will be used for each pairwise comparison with placebo, ie, there will be no adjustments for multiplicity since this is a Phase 2 study.

7.7.1 Subject Disposition

Subject disposition will be summarized by treatment group and will include subjects that enrolled, were randomly assigned, discontinued, and completed the study. For discontinued subjects, the reasons for discontinuation will be summarized.

7.7.2 Analyses of Demographic and Baseline Characteristics

Demographic and baseline characteristics such as age, gender, race, body weight, height, body mass index, and medical history will be summarized by treatment group using descriptive statistics.

7.7.3 Analysis of Platelet Response

The primary efficacy endpoint will be summarized as overall platelet response rate (ORR) by treatment group and analyzed using Fisher's exact test to compare the difference in ORR between each active treatment group and placebo. A logistic regression model will also be performed on platelet response and include treatment, baseline platelet count and prior TPO-receptor agonist use, provided there are enough subjects in each subgroup. The odds ratio for the treatment effect compared to placebo (together with 95% CI and p-value) will be provided.

Summary statistics will be provided on the number (%) of subjects achieving platelet response by each treatment group and the combined active treatment group. Fisher's exact test on the differences in the ORR will therefore be provided for:

- Each active treatment group (200 mg BID, 400 mg BID) vs. placebo
- Combine active treatment groups vs. placebo
- 200 mg BID vs. 400 mg BID.

Furthermore, summary statistics will be provided on the number (%) of subjects achieving platelet response by each treatment group and the subgroups defined in [Section 7.6](#).

A subject will be classified as a platelet responder if subject shows at least 1 platelet count $\geq 30,000/\mu\text{L}$ and doubling the baseline (average of 2 previous counts), at any visit during treatment period, without use of rescue medication. The ITT analysis set will be used in the analysis of the primary endpoint.

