5.1 Method of Assigning Subjects to Treatment Groups

Subjects will be randomly assigned in a 2:2:1 ratio to receive SKI-O-703 200 mg BID, SKI-O-703 400 mg BID, or matching placebo. A subset of at least 20 subjects will be randomized to undergo PK/PD assessments at a selected number of sites. An interactive voice response system (IVRS) will be used to administer the randomization schedule. The randomization schedule will be generated using SAS software Version 9.4 or later (SAS Institute Inc., Cary, North Carolina) for IVRS, which will link sequential subject randomization numbers to treatment codes. The randomization will be stratified to balance subjects with prior TPO-receptor agonist use (yes/no) and degree of baseline thrombocytopenia (ie, baseline platelet count < or \geq 15,000/ μ L). It will also use an appropriate block size, which will not be revealed.

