7.4 Sample Size Calculations

A minimum of 60 subjects will be enrolled in the study. Subjects will receive either 200 mg BID or 400 mg BID of SKI-O-703 or placebo in a 2:2:1 ratio.

Based on [Podolanczuk et al \(2009\)](#) at least 50% of subjects in the active treatment group will be responders (R). A sample size of 24 subjects per active treatment group and 12 subjects in the placebo group will provide approximately 82.7% power to detect a difference between response rates of 50% and 1% in the active treatment and placebo groups, respectively, at the 2-sided 5% significance level. The test statistic used in the sample size calculation was the 2-sided Fisher's Exact test using the normal approximation method.

Subjects that do not receive the study drug or do not provide at least 1 post baseline measurement will be excluded from the analysis above and replaced.

There will be no adjustment for multiple comparisons. The sample size calculation was performed using PASS 15 Power Analysis and Sample Size Software (2017). NCSS, LLC. Kaysville, Utah, USA, ncss.com/software/pass.

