### 4.2. Baseline Definition and Study Day

For platelet count related endpoints, baseline will be defined as the lowest platelet count within 1 month prior to or on the date that the first dose of study drug (SKI-O-703 or placebo) is taken. Data from Central lab will be used first. Otherwise, baseline will be defined as the last non-missing evaluation prior to or on the date that the first dose of study drug (SKI-O-703 or placebo) is taken.

The study day will be calculated as:

- Study day = assessment date - first dose of study drug (SKI-O-703 or placebo) date + 1, if assessment date is on or after the first dose date.
- Study day = assessment date – first dose of study drug (SKI-O-703 or placebo) date, if assessment date is prior to the first dose date.

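### Randomisation is stratified on two factors, but the primary Fisher test ignores the strata, and the one model adjusting for both has an infinite odds ratio versus placebo if placebo has no responders

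*Protocol*

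**What the plan says.** Protocol 5.1: "The randomization will be stratified to balance subjects with prior TPO-receptor agonist use (yes/no) and degree of baseline thrombocytopenia", with the platelet cut at 15,000/µL. SAP 4.5 repeats this. The result is four strata.

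Protocol 7.7.3: the response rate is "analyzed using Fisher's exact test to compare the difference in ORR" for each active group against placebo. SAP 8.1.1 also takes its p-value from Fisher's test. Neither brings in the strata. Protocol 7.4 sized the trial with the same kind of test, the "2-sided Fisher's Exact test using the normal approximation method".

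Both sections add a logistic regression of response on treatment, baseline platelet count and prior TPO-receptor agonist use. The Protocol makes it conditional on sufficient numbers per subgroup; SAP 8.1.1 drops that condition. The sensitivity analyses in SAP 8.1.2 reuse the model.

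For platelet endpoints, SAP 4.2 says "baseline will be defined as the lowest platelet count within 1 month prior to or on the date that the first dose" is taken. SAP 3.2.1 and 8.1 describe the baseline in the endpoint as a mean of two earlier counts. Neither document says which count sets the randomisation stratum. The 15,000/µL category appears in the baseline table (SAP 6.2) and the subgroup table (Protocol 7.6, SAP 8.4).

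**The concern.** Stratifying on factors thought to be prognostic and then testing without them discards some of the precision that the design bought. It also makes the unstratified test more conservative when the factors matter. The usual answer is that a covariate-adjusted model stands beside the simple test. Here that model is fragile under the trial's own planning assumption, because a near-zero placebo rate in 12 patients usually means no placebo responders at all. An adjusted estimate and p-value could then be missing or unusable just when the drug looks best.

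A second and separate matter is whether the platelet category in the tables is the one used at randomisation.

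**Working it through.** **Inputs.** From Protocol 7.4: "A sample size of 24 subjects per active treatment group and 12 subjects in the placebo group", response rates 50% and 1%, two-sided 5%, stated power 82.7% (82.74% in SAP 4.4). The documents give no stratum sizes, no prognostic effects and no block size, so those below are assumptions.

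**The plan's own figure.** Pooled normal approximation with continuity correction:

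- pooled rate = (24×0.50 + 12×0.01)/36 = 0.3367
- SE under the null = √(0.3367×0.6633×(1/24 + 1/12)) = 0.1671
- SE under the alternative = √(0.25/24 + 0.0099/12) = 0.1060
- correction = (1/24 + 1/12)/2 = 0.0625
- power = Φ((0.49 − 0.0625 − 1.96×0.1671)/0.1060) = Φ(0.943) = 82.7%

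The figure is reproduced. Full enumeration of the two-sided Fisher test at the same rates gives 93.9%, so the planned test has more power at those rates than stated. At a 10% placebo rate the enumeration gives 65.1%.

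**The adjusted model.** With no placebo responders and at least one active responder, the maximum-likelihood odds ratio versus placebo is infinite. The chance of no responders among 12 is (1 − p)^12:

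- p = 1%: 0.99^12 = 88.6%
- p = 5%: 0.95^12 = 54.0%
- p = 10%: 0.90^12 = 28.2%

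Fisher's test copes: with 0 of 12 on placebo it is significant from 8 of 24 on active. An exact stratified test copes too.

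**Power of an exact stratified test.** Condition on the responder total in each stratum. The number of active responders is then a sum of independent hypergeometric variables, and the two-sided p-value is the total probability of outcomes no more likely than the one observed. Simulation with 20,000 trials per row, four equal strata of 6 active and 3 placebo, active rate 50%:

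| Placebo rate | Odds ratio per factor | Fisher | Exact stratified |
|---|---|---|---|
| 1% (planned) | 1 | 93.9% | 94.0% |
| 1% | 2 | 94.1% | 94.6% |
| 1% | 4 | 95.1% | 96.3% |
| 1% | 8 | 95.7% | 97.9% |
| 10% (assumed) | 1 | 65.7% | 66.4% |
| 10% | 2 | 65.4% | 67.4% |
| 10% | 4 | 65.5% | 71.1% |
| 10% | 8 | 66.4% | 77.5% |

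Fixed equal strata flatter the stratified test. With 60 patients allocated 2:2:1 in stratified blocks of 5, so that stratum sizes vary, the difference (stratified minus Fisher) ran from −0.4 to +1.8 points at 50% versus 1%, and from −0.8 to +6.4 points at 50% versus 10%. Null rejection was about 3%.

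**Type I error.** By enumeration, Fisher's actual size is 1.6%, 2.5%, 2.7% and 3.0% at common rates of 10%, 20%, 30% and 50%. In the equal-strata simulation at a common rate of 20%, Fisher and the stratified test rejected 2.5% and 2.6% with non-prognostic strata, and 1.7% and 2.2% with an odds ratio of 4 per factor. Both are valid.

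**Baseline against stratum.** If the count that set the stratum is among those from which SAP 4.2 takes the minimum, patients can only move down. As an illustration, suppose a screening count set the stratum and a Day 1 count is also in the window. Take lognormal counts with median 15,000, between-patient log-SD 0.5 and within-patient log-SD 0.2 to 0.4 (all assumed). Then 9% to 15% of all patients move from the upper to the lower category. If the stratum was itself set from the lowest count over the same window, none would move.

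**The case against.** The case for the plan is a fair one. Both stratification factors are in a prespecified model of the primary endpoint, so it would be wrong to infer that the plan never adjusts for them. Fisher's test uses every patient, holds its level with 12 placebo patients and matches the test used for sizing. At the planned rates its exact power is already 93.9%.

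Nor is a stratified test free. A stratum without placebo patients contributes nothing to it. With non-prognostic strata, a fixed layout of active 10/7/3/4 and placebo 7/5/0/0 gave Fisher 65.5% against 57.6% stratified at a 10% placebo rate, and 94.0% against 90.4% at 1%. A layout of active 10/8/4/2 and placebo 6/5/1/0 gave 65.4% against 59.5% at 10%.

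Most of this stands. It rules out saying that Fisher's test has no merit, or that changing it can never lose power. Those losses do need unusually sparse layouts; under stratified blocks the loss stayed below 1 point. The defence based on the logistic model is the weak part: that model is additional, does not use the stratum as randomised and has no stated fallback under separation.

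**Conclusion.** The point holds as a modest, inexpensive improvement, not as a flaw that invalidates the primary test. The primary analysis does not follow the stratified design, and at the planned 1% placebo rate the only adjusted model has an 88.6% chance of facing a placebo group with no responders.

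The gain from an exact stratified test is about 0 to 2 points at 50% versus 1%. It is about 1 to 6 points if placebo response is nearer 10% and each factor has an odds ratio of 2 to 4. Those last values are assumptions. A reader might infer a large power loss, but the documents plan for rates at which it is small and give no prognostic effects to support more.

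A reader might also infer that the lowest-count baseline will break the strata and weaken the primary test. The documents support neither step. The stratifying count is unspecified, so the two may or may not agree, and the category never enters the Fisher test. What it can affect is the baseline table, the subgroup table and the logistic covariate.

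**What to change.** - For each dose against placebo, prespecify an exact stratified test (conditional, of Cochran-Mantel-Haenszel type) or exact logistic regression conditioning on the four strata as randomised. Make it primary with Fisher supportive. Failing that, make it the key supportive analysis, replacing maximum-likelihood logistic regression when there is separation.
- State what happens to strata with no placebo patients, for example a pooling rule fixed before unblinding.
- State which platelet count set the IVRS stratum, use the IVRS strata for the platelet-count and TPO-receptor agonist subgroups, and reconcile the baseline in SAP 4.2 with SAP 3.2.1 and 8.1.

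The cost is SAP wording and one exact procedure, with no new data. The price in power is usually under 1 point if the strata are not prognostic, and more if some strata have no placebo patients.

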7.7.4 Analysis of Secondary Endpoints

For each binary endpoint (ie, definition of subject achieving 2 or more consecutive platelet counts), a logistic regression model will be performed and include treatment, baseline platelet count and prior TPO-receptor agonist use, provided there are enough subjects in each

subgroup. The odds ratio for the treatment effect compared to placebo (together with 95% CI and p-value) will be provided.

Time to platelet response will be estimated using the Kaplan-Meier method. Each active treatment group curve will be compared against placebo curve using log-rank test. In addition, a proportional hazard model will be implemented as well with treatment, baseline platelet count, and prior TPO-receptor agonist use.

Change from baseline in the average of the last 2 platelet counts will be analyzed using an analysis of covariance with baseline platelets count as covariate, treatment, and prior TPO-receptor agonist use. Each active treatment group will be compared with placebo.

Summary statistics of the following subjects will be provided by each treatment group:

- Subjects receiving rescue medication during the treatment period
- Subjects with Grade 2 or higher non-skin bleeding event during the treatment or follow-up period

A subject will be considered to have an event if the event was observed at least once during the treatment period or follow-up period as mentioned above.

7.7.5 Analyses of Exploratory Endpoints

Peak platelet will be summarized by treatment groups. The median peak platelet, and the lower and upper quartile will be provided by treatment group. The difference in median peak platelet will be calculated for:

- Each active treatment group (200 mg BID, 400 mg BID) vs. placebo
- Combined active treatment groups vs. placebo
- 200 mg BID vs. 400 mg BID

Bleeding score will be summarized by treatment group and the combined active treatment groups.

7.7.6 Pharmacokinetic/Pharmacodynamic Analyses

7.7.6.1 Pharmacokinetic Analyses

Plasma concentrations of SKI-O-592 and its metabolites (M2 and M4) will be listed and summarized separately for each treatment and day at each nominal time point using descriptive statistics (number of observations [n], mean, SD, coefficient of variation [CV], minimum, median, and maximum). Individual and mean plasma concentration versus time profiles will be plotted for each treatment and day.

PK parameters for SKI-O-592 and its metabolites will be calculated using noncompartmental methods. Descriptive statistics (n, geometric mean, geometric CV, mean, SD, CV, minimum, median, and maximum) for the PK parameters for SKI-O-592 and its metabolites will be presented for each treatment and day. Treatment comparisons will be performed as deemed appropriate.

7.7.6.2 Pharmacodynamic Analyses

Absolute and percentage change from baseline in the percentage of activated CD63+ basophils in peripheral blood will be listed and summarized separately for each treatment and day at each nominal time point using descriptive statistics (number of observations [n], mean, SD, CV, minimum, median, and maximum). Individual, mean absolute and percentage change from baseline in the percentage of activated CD63+ basophils will be plotted versus time for each treatment and day.

PD parameters for the percentage of activated CD63+ basophils will be calculated using non-compartmental methods. Descriptive statistics (n, mean, SD, CV, minimum, median, and maximum) for the PD parameters will be presented for each treatment and day. Treatment comparisons will be performed as deemed appropriate.

7.7.6.3 Exploratory PK/PD Analyses

PK/PD relationship between plasma concentrations of SKI-O-592, M2, and M4 and change from baseline in the percentage of activated CD63+ basophils in peripheral blood on Day 1 and Week 12 will be assessed. Individual and mean plasma concentrations of SKI-O-592, M2, and M4 will be plotted versus change from baseline in the percentage of activated CD63+ basophils in peripheral blood on Day 1 and Week 12.

Exploratory PK/PD modeling may also be performed; full details will be provided in a separate Statistical Analysis Plan.

7.7.7 Safety Analyses

Continuous parameters (such as laboratory measurements, ECG results, and vital signs) will be summarized separately for each treatment at each nominal time point using descriptive statistics (mean, SD, minimum, median, and maximum).

Discrete parameters (such as deaths, SAEs, AEs, concomitant medications, and physical examination results) will be summarized separately for each treatment at each nominal time point using frequency counts and percentages. All AEs, SAEs, drug-related AEs, and drug-related SAEs will be summarized using the worst grade per NCI CTCAE v5.0 by system organ class and preferred term. All safety data will be listed.

Safety results will be summarized using the safety set by treatment groups and the combined active treatment group, unless otherwise specified.

7.7.8 Interim Analyses

An unblinded interim safety and PK data review will be performed by the DMC once the subjects in the safety run-in period complete their Day 8 (± 2 days) assessments. Subjects in the safety run-in period will continue to be dosed whilst the interim analysis is being conducted. However, further enrollment in each treatment group will only resume after safety and PK data of the first week for the first 5 subjects are reviewed and considered satisfactory by the DMC.

8 Data Quality Assurance

This study will be conducted according to the ICH E6(R2) risk and quality processes described in the applicable procedural documents. The quality management approach to be implemented in this study will be documented and will comply with the current ICH guidance on quality and risk management ([ICH 2005](#)).

8.1 Data Management

As part of the responsibilities assumed by participating in the study, the investigator agrees to maintain adequate case histories for the subjects treated as part of the research under this protocol. The investigator agrees to maintain accurate eCRFs and source documentation as part of the case histories. These source documents may include laboratory reports and ECG strips.

Investigative site personnel will enter subject data into Oracle™Clinical Remote Data Capture. The analysis data sets will be a combination of these data and data from other sources (eg, laboratory data).

Clinical data management will be performed in accordance with applicable sponsor standards and data cleaning procedures to ensure the integrity of the data, eg, removing errors and inconsistencies in the data. Adverse events and concomitant medication terms will be coded using MedDRA Version 20.0 or later, an internal validated medication dictionary.

After database lock, each study site will receive a CD-ROM containing all of their site specific eCRF data as entered into Oracle Clinical Remote Data Capture for the study, including full discrepancy and audit history. Additionally, a CD-ROM copy of all of the study site's data from the study will be created and sent to the sponsor for storage. PPD will maintain a duplicate CD-ROM copy for their records. In all cases, subject initials will not be collected or transmitted to the sponsor.

9 Ethics

9.1 Independent Ethics Committee or Institutional Review Board

Federal regulations and the ICH guidelines require that approval be obtained from an IRB/IEC before participation of human subjects in research studies. Before study onset, the protocol, informed consent, advertisements to be used for the recruitment of study subjects, and any other written information regarding this study to be provided to the subject or the subject's legal guardian must be approved by the IRB/IEC. Documentation of all IRB/IEC approvals and of the IRB/IEC compliance with ICH harmonised tripartite guideline E6(R2): Good Clinical Practice (GCP) will be maintained by the site and will be available for review by the sponsor or its designee.

All IRB/IEC approvals should be signed by the IRB/IEC chairman or designee and must identify the IRB/IEC name and address, the clinical protocol by title or protocol number or both, and the date approval or a favorable opinion was granted.

The investigator is responsible for providing written summaries of the progress and status of the study at intervals not exceeding 1 year or otherwise specified by the IRB/IEC. The investigator must promptly supply the sponsor or its designee, the IRB/IEC, and, where applicable, the institution, with written reports on any changes significantly affecting the conduct of the study or increasing the risk to subjects.

9.2 Ethical Conduct of the Study

The study will be performed in accordance with the ethical principles that have their origin in the Declaration of Helsinki, ICH GCP, the protocol, and all applicable regulations.

9.3 Subject Information and Consent

A written informed consent in compliance with the respective applicable regulatory authority regulations shall be obtained from each subject before entering the study or performing any unusual or nonroutine procedure that involves risk to the subject. An informed consent template may be provided by the sponsor to investigative sites. If any institution-specific modifications to study-related procedures are proposed or made by the site, the consent should be reviewed by the sponsor or its designee or both before IRB/IEC submission. Once reviewed, the consent will be submitted by the investigator to his or her IRB/IEC for review

and approval before the start of the study. If the ICF is revised during the course of the study, all active participating subjects must sign the revised form.

Before recruitment and enrollment, each prospective subject or his or her legal guardian will be given a full explanation of the study and be allowed to read the approved ICF. Once the investigator is assured that the subject/legal guardian understands the implications of participating in the study, the subject/legal guardian will be asked to give consent to participate in the study by signing the ICF.

The investigator shall retain the signed original ICF(s) and give a copy of the signed original form to the subject or legal guardian.

10 Investigator's Obligations

The following administrative items are meant to guide the investigator in the conduct of the study but may be changed based on industry and government standard operating procedures, working practice documents, or guidelines. Changes will be reported to the IRB/IEC but will not result in protocol amendments.

